**Appendix D: International Working Group (IWG) Response Criteria in Myelodysplasia (Cheson, 2006) (Continued)**

Altering Disease Natural History	
Disease transformation	Transformation to AML (30% or more blasts)
Relapse after CR or PR	At least one of the following: 
 
• Return to pretreatment bone marrow blast %
 
• Decrement of <math>\geq 50\%</math> from maximum remission/response levels in granulocytes or platelets
 
• Reduction in Hgb concentration by <math>\geq 1.5</math> g/dL or transfusion dependence
 

Cytogenetic Response	
Complete	Disappearance of the chromosomal abnormality without appearance of new ones
Partial	At least 50% reduction of the chromosomal abnormality
Hematological Improvement (HI)	
Erythroid response (HI-E) (Pretreatment $< 11$ g/dL)	Hgb increase by $\geq 1.5$ g/dL Relevant reduction of units of RBC transfusions by an absolute number of at least 4 RBC transfusions/8 weeks compared with the pretreatment transfusion number in the previous 8 weeks. Only RBC transfusions given for a Hgb of $\leq 9.0$ g/dL pretreatment will count in the RBC transfusion evaluation
Platelet response (HI-P) (Pretreatment $< 100 \times 10^9/L$ )	Absolute increase of $\geq 30 \times 10^9/L$ for patients starting with $> 20 \times 10^9/L$ Increase from $< 20 \times 10^9/L$ to $> 20 \times 10^9/L$ and by at least 100%
Neutrophil response (HI-N) (Pretreatment $< 1.0 \times 10^9/L$ )	At least 100% increase and an absolute increase of $> 0.5 \times 10^9/L$
Progression/relapse after HI	At least one of the following: 
 
• At least 50% decrement from maximum response levels in granulocytes or platelets
 
• Reduction in Hgb by <math>\geq 1.5</math> g/dL
 
• Transfusion dependence
 

AML = acute myeloid leukemia; Hgb = hemoglobin; RBC = red blood cell  
 Source: Cheson BD, Greenberg PL, Bennett JM, Löwenberg B, Wijermans PW, Nimer SD, et al. Clinical application and proposal for modification of the International Working Group (IWG) response criteria in myelodysplasia. Blood. 2006; 108(2): 419-25.

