The End of Trial is defined as either the date of the last subject last visit for the completion of post-treatment follow-up, or the date of receipt of the last data point from the last subject that is required for primary, secondary and/or exploratory analyses, whichever is the later date. See Section 3.3 of the protocol.

Study Treatments

Subjects will be randomized 1:1 to receive either:

Treatment Arm A: Subcutaneous azacitidine (75 mg/m² daily for 7 days every 4 weeks [Q4W]) in combination with intravenous (IV) durvalumab at a dose of 1500 mg on Day 1 Q4W,

Or

Treatment Arm B: Subcutaneous azacitidine alone at the dose of 75 mg/m² daily for 7 days Q4W.

Table 2: Study Endpoints

Endpoint	Name	Description
MDS Cohort		
Primary	Overall response rate	Proportion of MDS subjects achieving an overall response (CR, mCR, PR or HI), based on IWG 2006 response criteria (Appendix 17.2).
Secondary	Time to response	Time from randomization to first documented response according to IWG 2006 response criteria (Appendix 17.2).
	Relapse-free survival	Time from the date CR or PR is first documented until the date of documented relapse, death from any cause, or lost to follow-up, whichever occurs first according to IWG 2006 response criteria (Appendix 17.2).
	Cytogenetic response (CyCR)	Proportion of subjects achieving complete cytogenetic response or partial cytogenetic response according to IWG 2006 response criteria (Appendix 17.2).
	Progression-free survival (PFS)	Time from randomization to the first documented PD, relapse or death due to any cause, whichever occurs first.
	Duration of response	Duration of response is defined as the time from first response observed (CR, mCR, PR or HI) until relapse, PD or death as defined by the IWG 2006 criteria (Appendix 17.2).
	Time to AML transformation	Time from randomization to AML transformation defined by at least 30% of myeloblasts either in the bone marrow or the peripheral blood.
	Transformation to AML	Proportion of subjects with disease transformation to AML.
AML Cohort		
Primary	Overall response rate	Proportion of AML subjects achieving an overall response (CR or CRi) based on modified IWG 2003 response criteria for AML. (Appendix 17.3).
Secondary	Time to response	Time from randomization to first documented response based on modified IWG 2003 response criteria for AML (Appendix 17.3).

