10.1. Primary Efficacy Endpoint

The primary efficacy endpoint is the ORR and will be programmatically derived using the results/assessments generated by the central morphologic/cytogenetic and hematology laboratories. In case no central hematology results are available within +/- 8 days of bone marrow samples, local hematology results might be used if available. This analysis will be conducted after completion of the Stage 1 and Stage 2 portions of the study. A subject is considered evaluable for response if they have undergone at least one disease status assessment following treatment Cycle 6. Subjects who discontinue from the treatment phase before the first post baseline efficacy assessment (following treatment Cycle 3) will be replaced unless the subject had a documented progression of their disease or died and will be considered as non-responders. If one post baseline disease assessment is performed, this assessment would be considered for response.

The difference of the proportions for overall response between the azacitidine alone and combination therapy arms will be tested using a standard Wald asymptotic two-sided test with unpooled estimate of variance and presented along with corresponding two-sided 95% CIs.

The hypothesis tested will be:

$$H_0: d = 0$$

versus

$$H_a: d \neq 0,$$

Where $d = p_1 - p_2$ is difference in overall response rate in the combination therapy arm (p_1) versus the overall response rate in the monotherapy arm (p_2).

The test statistic is

$$z = \hat{d}/se(\hat{d})$$

Where, the standard error is computed from the sample proportions as

$$se(\hat{d}) = \sqrt{\frac{\hat{p}_1(1 - \hat{p}_1)}{n_1} + \frac{\hat{p}_2(1 - \hat{p}_2)}{n_2}}$$

Where \hat{p}_1 (respectively \hat{p}_2) is the estimated response rate in the combination therapy arm (respectively monotherapy arm) and is derived as the observed response rates in respective arms.

Myelodysplastic Syndromes Cohort

For the MDS cohort, the primary efficacy endpoint is the proportion of subjects achieving an overall response rate (defined as CR, PR, mCR, and/or HI) as determined using the International Working Group (IWG) 2006 response criteria for MDS ([Appendix 17.2](#)). The ORR will be summarized together with two-sided 95% CI. Subjects discontinued before 6-cycle treatment without achieving overall response will be counted as nonresponders.

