17.2. International Working Group (IWG) Response Criteria in Myelodysplasia (Cheson, 2006)

Altering Disease Natural History	
Complete remission (CR)	
 ▪ BM Blasts \leq 5% 
AND
 
 ▪ All of the following peripheral blood values met: 
 ▪ Hemoglobin \geq 11 g/dL ▪ Platelets \geq 100 x10⁹/L ▪ ANC \geq 1.0 x10⁹/L ▪ Peripheral Blasts=0% 
Labs must meet criterion for at least 28 consecutive days. If not confirmed for 28 days then response should be mCR.
 
In addition
 
 ▪ The 7/3 rule should be applied to Hemoglobin. ▪ Platelets collected 3 days period following Platelet transfusion will not be used - ANC values that must be at least 14 days following a G-CSF application
Partial remission (PR)	
 ▪ BM Blasts decreased by \geq 50% over pretreatment but still $>$ 5% 
AND
 
 ▪ All of the following peripheral blood values met: 
 ▪ Hemoglobin \geq 11 g/dL ▪ Platelets \geq 100 x10⁹/L ▪ ANC \geq 1.0 x10⁹/L ▪ Peripheral Blasts=0% 
Labs Must meet criterion for at least 28 consecutive days.
 
In addition
 
 ▪ The 7/3 rule should be applied to Hemoglobin. ▪ Platelets collected 3 days period following Platelet transfusion will not be used 
ANC values that must be at least 14 days following a G-CSF application

Marrow CR	
 ▪ Bone marrow: $\leq 5\%$ myeloblasts and decrease by $\geq 50\%$ over pretreatment with baseline BM blast $>5\%$ 
AND
 
 ▪ Not all of the following peripheral blood values met or none are met: 
 ▪ Hemoglobin ≥ 11 g/dL ▪ Platelets $\geq 100 \times 10^9/L$ ▪ ANC $\geq 1.0 \times 10^9/L$ ▪ Peripheral Blasts=0% 
Peripheral blood: if HI responses, they will be noted in addition to marrow CR

Stable disease (SD)	Any evaluable time point where criteria for all other response categories (i.e., CR, PR, PD, Failure due to death, Not Assessable) are not met
Failure	Death during treatment

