Erythroid response (HI-E) (Pretreatment < 11 g/dL)	
 ▪ Hgb increase by \geq 1.5 g/dL in \geq 8 weeks 
OR
 
 ▪ Relevant reduction of units of RBC transfusions by an absolute number of at least 4 RBC transfusions/8 weeks compared with the pretreatment transfusion number in the previous 8 weeks. Only RBC transfusions given for a Hgb of \leq 9.0 g/dL pretreatment will count in the RBC transfusion evaluation 
 ▪ For Hgb, 7/3 rule should be applied first
Platelet response (HI-P) (Pretreatment < $100 \times 10^9/L$)	
 ▪ in \geq 8 weeks Absolute increase of $\geq 30 \times 10^9/L$ for patients starting with $> 20 \times 10^9/L$ 
OR
 
 ▪ Increase from $\leq 20 \times 10^9/L$ to $> 20 \times 10^9/L$ and by at least 100%

Neutrophil response (HI-N) (Pretreatment $< 1.0 \times 10^9/L$)	
 ▪ in ≥ 8 weeks At least 100% increase and an absolute increase from mean of pre-dose of $> 0.5 \times 10^9/L$
---	---

AML = acute myeloid leukemia; Hgb = hemoglobin; RBC = red blood cell

Source: Cheson BD, Greenberg PL, Bennett JM, Löwenberg B, Wijermans PW, Nimer SD, et al. Clinical application and proposal for modification of the International Working Group (IWG) response criteria in myelodysplasia. Blood. 2006; 108(2): 419-25.

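### As laid out in SAP 17.2, the platelet-response (HI-P) limb for subjects starting at platelets of 20 or below has no duration or confirmation rule, so a single count that is above 20 and at least double baseline makes an MDS primary-endpoint responder

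*SAP*

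**What the plan says.** SAP 10.1 takes the MDS primary endpoint as overall response, "defined as CR, PR, mCR, and/or HI", derived by program from central laboratory results. SAP Table 2 agrees: "Proportion of MDS subjects achieving an overall response (CR, mCR, PR or HI". HI without any marrow response is therefore enough.

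The HI-P row of SAP 17.2 has two bullets joined by OR (platelets in 10⁹/L):

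- Start above 20: a rise of at least 30. The 8-week words stand inside this bullet: "8 weeks Absolute increase of".
- Start at 20 or below: a rise "to $> 20 \times 10^9/L$ and by at least 100" percent. There are no duration words.

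Three other rows help in reading this one:

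- HI-N opens with the same phrase: "8 weeks At least 100% increase and an absolute increase from mean of pre-dose of".
- CR and PR each carry a 28-day condition; for CR it reads "Labs must meet criterion for at least 28 consecutive days".
- CR and PR also exclude counts taken soon after a platelet transfusion: "Platelets collected 3 days period following Platelet transfusion will not be used". HI-P has no such line.

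Protocol Appendix D words the limb as "Increase from $< 20 \times 10^9/L$ to $> 20 \times 10^9/L$ and by at least 100" percent, again without a duration.

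**The concern.** A program written from the SAP text would accept one unsustained platelet count as a primary-endpoint response for a subject starting at 20 or below. A subject starting above 20 would have to satisfy an 8-week condition. The low-baseline limb is also where a doubling is smallest in absolute terms, so ordinary visit-to-visit variation, or a platelet transfusion (permitted under Protocol 8.1), can produce it. False responders would enter the ORR in both arms and dilute the 36% v 72% difference on which the cohort is sized. They would also enter time to response and duration of response, and the HI rate that SAP 10.2 reports for the AML cohort from the same table.

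**Working it through.** **The plan's own figure.** Inputs (SAP 4.3.1 and 10.1): 36% v 72%, 90% power, 5% level, two-sided, unpooled variance, 1:1 allocation.

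n per arm = (1.960 + 1.282)² × [0.36×0.64 + 0.72×0.28] / 0.36² = 35.02, so 36 per arm and 72 in total. This matches the SAP. Power at 36 per arm is 90.8%.

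**Count needed to qualify.** The limb needs a value above 20 and at least 2 × baseline. A baseline of 10 or less needs just above 20; 12 needs 24; 15 needs 30; 18 needs 36; 20 needs 40.

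**Number of counts.** Protocol 6.6.6.1 schedules Days 8, 15 and 22 of Cycle 1 (3), Days 1, 8, 15 and 22 of Cycle 2 (4), and Days 1 and 15 of Cycles 3–6 (8). Adding Cycle 7 Day 1 gives 16. Protocol 6.7.3 schedules response assessment after every third cycle, which is 2 by the end of Cycle 6. The SAP does not say which set HI-P uses.

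**False HI-P in a stable subject.** Assumptions, none from the documents: log-normal counts with constant mean m, independent readings, one baseline count of 20 or less, no transfusion. With s² = ln(1 + CV²) and threshold t = max(20, 2 × baseline):

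- chance per reading: p = 1 − Φ{[ln(t/m) + s²/2]/s}
- chance over k readings: 1 − (1 − p)^k, averaged over baselines of 20 or less

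Example: m = 12, CV 30%, so s = 0.294.

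- Baseline 12 (t = 24): p = 1 − Φ(2.51) = 0.6%, giving about 9% over 16 readings and 1.2% over 2.
- Baseline 9 (t = 20): p = 1 − Φ(1.89) = 3.0%, giving about 38% over 16 readings and 6% over 2.

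Averaged by simulation (200,000 subjects):

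| True mean | Counts used | CV 20% | 25% | 30% | 40% |
|---|---|---|---|---|---|
| 12 | 2 | 0.2% | 1% | 3% | 7.5% |
| 12 | 16 | 2% | 8% | 19% | 42% |
| 15 | 2 | 1% | 3% | 7% | 15% |
| 15 | 16 | 6% | 19% | 33% | 57% |
| either | held 8 weeks | <0.1% | <0.1% | <0.1% | <0.1% |

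The last row reads the 8-week phrase as requiring the rise to be held. If it were read as any one count at week 8 or later, the rates would be about 1–28% (mean 12) and 4–44% (mean 15).

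**Effect on power.** Let f be the share starting at 20 or below and π the false HI-P chance, equal in both arms, with q = fπ. Each observed rate becomes p + q(1 − p), so the difference becomes 0.36(1 − q).

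- f = 10%, π = 10%: 72.3% v 36.6%; 0.3564/0.1096 − 1.960 = 1.29; power 90.2%.
- f = 10%, π = 30%: 72.8% v 37.9%; 0.3492/0.1097 − 1.960 = 1.22; power 88.9%.
- f = 20%, π = 30%: power 86.9%.
- f = 30%, π = 50% (extreme): power 80.0%.

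**The case against.** The strongest reply is that the gap comes from layout. The 8-week phrase opens the HI-P cell and is followed by a capitalised word, exactly as in HI-N, so it may be a lead-in meant for both bullets. That is plausible, and the omission should not be called deliberate. It does not settle the matter: the text as laid out attaches the phrase to one bullet, and the SAP changed this limb's entry cut from below 20 to 20 or below without adding a duration. SAP 15 says only that derivations were aligned with the IWG criteria.

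A second reply is that HI is assessed every three cycles, so the 16-count rates are too high. This largely stands, and the two-assessment rates are given for that reason. The constant-mean model also ignores the early thrombocytopenia described in Protocol 7.2.2.1, and 7 of the 16 counts fall in Cycles 1–2. But the SAP does not restrict HI to those assessments. Its marrow-date windows concern the AML categories and the fallback to local hematology results.

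Two stronger readings are tempting and not supported. A reader might infer that any count above 20 makes a responder; the doubling requirement rules that out unless baseline is 10 or less. A reader might also infer that Protocol Appendix D has no time frame for any HI limb; its HI-E transfusion limb is counted per 8 weeks.

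**Conclusion.** The point holds as a gap in the written rule. The limb for starting counts of 20 or below has no duration or confirmation, no other section provides one, and the limb feeds the MDS primary endpoint. In stable subjects in this limb the false-response rate is about 0.2–15% with two assessments and 2–57% with 16 counts, against under 0.1% with an 8-week hold. These ranges rest on assumed CVs and means.

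The documents do not give the share of subjects starting at 20 or below, so the trial-level effect is illustrative: power of about 89–90% instead of 90.8% if that share is 10%. The error is expected to be similar in both arms. With equal true rates, equal misclassification leaves the observed rates equal, so a reader should not infer type I error inflation. Nor do the upper rates describe the cohort; they apply only within this limb and with every count used.

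**What to change.** In SAP 17.2, move the 8-week condition to a line above both HI-P bullets and word it as a sustained requirement, so that the limb for starting counts of 20 or below carries the same condition as the limb above 20 and HI-N. Apply to HI-P the platelet-transfusion exclusion already written for CR and PR.

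Do not go further and require every evaluable value over 56 days in all HI rows. On assumed hemoglobin SDs of 0.5–0.9 g/dL, that rule would reject 36–52% of subjects with a true sustained rise of 2.0 g/dL, and it does not fit the transfusion-count limb of HI-E.

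Cost: SAP wording, and a few unsustained HI-P responses no longer count.

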Myeloid growth factors (G-CSF and GM-CSF) may be given per Investigator's discretion for the treatment of neutropenic fever/infections as well as for secondary prophylaxis if the subject had a previous event of neutropenic fever/infection or neutropenia Grade 4 during the treatment phase of the study and the safety of the subject is considered jeopardized by subsequent episodes of neutropenic fever/infections or Grade 4 neutropenia.

For subjects who develop an ANC  $< 0.5 \times 10^9/L$  (or per institutional standards), administration of prophylactic fluoroquinolone antibiotics (eg, ciprofloxacin or levofloxacin) or other recognized prophylactic antibiotics may be considered and documented as a concomitant medication on the appropriate subject's eCRF. If neutropenic fever/infection occurs, treatment should consist of a broad spectrum antibiotic, and if the Investigator deems the use of a myeloid growth factor to be medically important, myeloid growth factors may also be administered. For secondary prophylaxis with myeloid growth factors, the dose modification guidelines detailed in Section 7.2.2 remain applicable. Discontinuation of secondary prophylaxis with myeloid growth factors should be considered by the Investigator as clinically appropriate.

Concurrent systemic corticosteroids for non-cancer-related conditions are allowed (eg, insulin for diabetes and hormone replacement therapy), provided the subject is on a stable or decreasing dose for  $\geq 1$  week prior to the first dose of IP, and provided the exclusion criteria #17 is met. Initiation, modification, and/or discontinuation of corticosteroids during the treatment phase of the study is discouraged and should be discussed with the sponsor's medical monitor first whenever possible.

For AML subjects, the use of hydroxyurea is permitted up to 2 weeks prior to the screening hematology sample and is prohibited during the whole study participation.

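### In the MDS primary endpoint, HI-P and HI-N carry no exclusion for platelet values after transfusion or ANC values after growth factor, although the same SAP appendix applies those exclusions to CR and PR

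*SAP*

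**What the plan says.** **HI counts on its own.** SAP 4.1, Table 2 defines the MDS primary endpoint as "Proportion of MDS subjects achieving an overall response (CR, mCR, PR or HI"), and SAP 10.1 repeats the same components. Protocol Table 2 and Section 9.6.1.1.1 agree. Response is derived by program from central laboratory results, with local haematology as a fallback (SAP 10.1).

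**CR and PR are protected.** In SAP 17.2 both rows require the blood values to hold for 28 consecutive days and then add three filters: the 7/3 rule for haemoglobin, "Platelets collected 3 days period following Platelet transfusion will not be used", and "ANC values that must be at least 14 days following a G-CSF application".

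**HI is protected only for haemoglobin.** Under HI-E, SAP 17.2 says "For Hgb, 7/3 rule should be applied first". The HI-P row (pretreatment platelets below 100 × 10⁹/L) and the HI-N row (pretreatment ANC below 1.0 × 10⁹/L) have no corresponding line. HI-N reads "At least 100% increase and an absolute increase from mean of pre-dose of" more than 0.5 × 10⁹/L.

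**Support is allowed.** Protocol 8.1 permits platelet transfusion by institutional standards. It permits G-CSF and GM-CSF at the investigator's discretion for neutropenic fever or infection, and also "for secondary prophylaxis if the subject had a previous event of neutropenic fever/infection or neutropenia Grade 4" during treatment where the subject's safety is considered at risk.

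**The concern.** The SAP treats supportive care as a contaminant of the blood count for MDS CR and PR, for HI-E and, in SAP 17.3, for AML CR (no platelet transfusion in the preceding 7 days). It does not do so for HI-P and HI-N, which carry equal weight in the MDS primary endpoint. The subjects open to these two categories started with low platelets or low neutrophils, so they are the ones most likely to be supported.

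A platelet count held up by repeated transfusion, or an ANC held up by continuing prophylaxis, could therefore be scored as a response to study treatment. The reverse can also happen: a baseline platelet count raised by transfusion makes the required rise harder to reach. For HI-N the baseline is less exposed, because exclusion criterion 5 bars G-CSF in the 28 days before first dose.

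The same rows feed the futility comparison at the interim analysis, time to response and duration of response in the MDS cohort, and the HI rate in the AML cohort.

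**Working it through.** **1. Does any other section supply the missing rule?**

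| Place | What it covers |
|---|---|
| SAP 17.2, CR and PR rows | haemoglobin, platelets, ANC |
| SAP 17.2, HI-E row | haemoglobin only |
| SAP 17.2, HI-P and HI-N rows | none |
| SAP 5.3.4 (baseline) | haemoglobin only |
| Protocol Appendix D | no platelet-value or ANC exclusion |
| Protocol 6.7.6 | discounts certain RBC transfusions only |
| Protocol 3.2.2.3 and 6.1.3 | platelet transfusions recorded and compared with the 56-day history; no values dropped, growth factors not mentioned |

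None does.

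**2. Does the 8-week wording close the gap?** From Cycle 3, haematology is scheduled on Days 1 and 15 (Protocol 6.6.6.1), so 56 days hold 56/14 = 4 intervals, that is four or five values. SAP 17.2 does not say whether all of them must qualify. As printed, the phrase stands on the first HI-P bullet ("weeks Absolute increase of" at least 30 × 10⁹/L) and not on the second (from 20 or below to above 20, and by at least 100%). The CR and PR rows keep their filters in addition to a 28-day duration rule, so the SAP itself does not treat duration as a substitute.

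**3. The plan's own sample size.** Inputs from SAP 4.3.1 and 10.1: 36% v 72%, two-sided 5%, 90% power, 1:1, Wald test with unpooled variance.

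n per arm = (1.960 + 1.282)² × (0.36×0.64 + 0.72×0.28) / 0.36² = 35.02, rounded up to 36, so N = 72. This matches. At 36 per arm the normal-approximation power is 90.8%; exact binomial enumeration of the same test gives 88.6%. With 36% in both arms, the exact chance of a significant result favouring the combination is 3.1%.

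**4. Illustration.** Let f be the assumed share of true non-responders scored as HI because of support. Observed ORR = p + (1 − p) × f. All results are exact enumerations at 36 per arm.

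True effect, same f in both arms:

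| f | ORR combination v control | Power |
|---|---|---|
| 0 | 72.0% v 36.0% | 88.6% |
| 5% | 73.4% v 39.2% | 86.1% |
| 10% | 74.8% v 42.4% | 83.3% |

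No true effect (p = 36% in both arms):

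| f control | f combination | ORR control v combination | Chance of significance favouring combination |
|---|---|---|---|
| 0 | 0 | 36.0% v 36.0% | 3.1% |
| 5% | 5% | 39.2% v 39.2% | 3.1% |
| 10% | 10% | 42.4% v 42.4% | 2.9% |
| 5% | 7% | 39.2% v 40.5% | 3.9% |
| 5% | 15% | 39.2% v 45.6% | 8.9% |
| 5% | 20% | 39.2% v 48.8% | 13.7% |
| 15% | 5% | 45.6% v 39.2% | 0.7% |

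Equal rates cost power but do not inflate type I error. Unequal rates move the result towards the arm with more false HI.

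**The case against.** The strongest reply is that the 8-week phrase already does the work. If it means a sustained rise, one transfused count or one course of G-CSF cannot qualify; counts would have to be raised at several visits two weeks apart. Secondary prophylaxis is also conditional on an earlier event and a judgement of risk, and the documents do not say how often either form of support recurs. Protocol 3.2.2.3 and 6.1.3 show an intention to take platelet transfusions into account when confirming response.

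Part of this stands. A reader might infer that a single transfused platelet count, or one G-CSF-driven ANC, makes a subject a responder. The documents do not establish that, because a sustained reading would remove isolated spikes. But they do not state that reading, it would not remove recurrent support, and as printed it misses the second HI-P bullet (the layout of these rows may have suffered in text extraction). The two protocol sections require recording and comparison; they exclude no value and say nothing on growth factors.

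A reader might also infer that the gap biases the trial towards the combination. The documents do not support that either. The trial is open-label and growth-factor use is discretionary, so use could differ by arm, but Protocol 3.2.2.2 anticipates no overlapping toxicity. More cytopenia in the combination arm would also lower counts and make a qualifying rise harder.

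**Conclusion.** Wrong as written, and the omission is certain: SAP 17.2 applies two exclusions to CR and PR and leaves them out of two other routes to the same primary endpoint. A program that follows the text could create false HI responders, or miss true HI-P responders whose baseline count was transfused.

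The effect on the result is not known. The documents give no transfusion or growth-factor rates, so neither size nor direction can be derived. The figures above rest on assumed values of f applied to all non-responders, although only those with low baseline platelets or ANC can reach HI-P or HI-N. At equal rates of 5% to 10%, the loss is about 2.5 to 5.3 percentage points of power (88.6 − 86.1; 88.6 − 83.3). At rates three times higher in one arm (5% v 15%), the chance of a false finding for the combination becomes 8.9% or 0.7%, depending on which arm has more. This is an inconsistency in specification that should be closed, not evidence that the primary comparison is biased.

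**What to change.** This is a change to an analysis rule only; what support subjects receive is unaffected. In SAP 17.2:

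- HI-P: apply the existing 3-day exclusion after platelet transfusion, to baseline and on-treatment values.
- HI-N: apply the existing 14-day exclusion after G-CSF, to baseline and on-treatment values.
- Treat GM-CSF in the same way as G-CSF, since Protocol 8.1 permits both and SAP 17.2 names only G-CSF.
- State that the 8-week wording means a sustained improvement and that it covers both HI-P bullets.

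The cost is a few lines of text and reuse of the CR/PR derivation code. The dates are already collected: transfusions under Protocol 6.7.6 and growth factors as concomitant medication under Protocol 8.1. The sample size stays at 72. Slightly fewer subjects may qualify for HI.
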